2. STUDY OBJECTIVES AND ENDPOINTS

2.1. Primary, Secondary, and Tertiary Study Objectives and Endpoints

The primary, secondary, and tertiary study objectives and endpoints are as follows:

Objectives	Endpoints
The primary objective of this study is to support the long-term safety of reslizumab 110 mg administered sc once every 4 weeks in patients 12 years of age and older with severe eosinophilic asthma that is inadequately controlled on standard-of-care treatment.	
The primary endpoint is frequency of all adverse events including serious adverse events.
 
The secondary safety endpoints for this study include the following:
 
• clinical laboratory test results
– hematology and chemistry results at baseline and at weeks 4 (chemistry only), 8, 24, and 36 or early withdrawal visit• local tolerability at the injection site at approximately 1 hour after study drug administration every 4 weeks throughout the study• vital signs measurements every 4 weeks throughout the study• concomitant medication usage every 4 weeks throughout the study
The secondary objective of this study is to evaluate the efficacy of reslizumab 110 mg administered sc once every 4 weeks in patients 12 years of age and older with severe eosinophilic asthma that is inadequately controlled on standard-of-care treatment.	
The secondary efficacy endpoints for this study include the following:
 
• clinical asthma exacerbation (CAE) and healthcare utilization (HCU)-related endpoints
– frequency of CAEs– frequency of asthma-specific hospital admissions– length of hospital stay and number of ICU days– frequency of asthma-specific emergency department visits– frequency of school/work days missed due to asthma• change from baseline in pre-bronchodilator FEV₁ measured using spirometry at weeks 0, 8, 24, and 36 or early withdrawal visit• change in daily morning ambulatory FEV₁ from baseline at each week through week 36 or early withdrawal, as measured by the handheld spirometry device• absolute and percent reduction in the daily OCS dose at

Objectives	Endpoints
	
weeks 20 and 36 or early withdrawal visit as compared with the dose at baseline (for patients on daily OCS at baseline)
 
 • change from baseline in total inhalations of reliever bronchodilator medication (eg, short-acting beta-agonist) measured using weekly averages until week 36 or early withdrawal visit • change from baseline in ACQ-6 score performed at weeks 0, 8, 24, and 36 or early withdrawal visit • change from baseline in AQLQ12+ score performed at weeks 0, 8, 24, and 36 or early withdrawal visit
	
The immunogenicity assessments for this study include the following:
 
 • ADA measurement at baseline and at weeks 8, 24, and 36 or early withdrawal visit to evaluate the long-term immunogenicity of sc reslizumab • ADA measurement at the EOS visit (19 weeks after the final dose) to evaluate immunogenicity after study drug washout
No tertiary or exploratory objectives.	No tertiary or exploratory endpoints.

ACQ-6=Asthma Control Questionnaire; ADA=anti-drug antibody; AQLQ12+=Asthma Quality of Life Questionnaire; EOS=end of study; FEV₁=forced expiratory volume in 1 second; FVC=forced vital capacity; ICU=intensive care unit; OCS=oral corticosteroids; [REDACTED]; SABA=short-acting beta-agonist; sc=subcutaneous

2.1.1. Justification of Primary Endpoint

The primary objective of this study is to support and obtain additional long-term safety data for sc administration of reslizumab treatment administered at a fixed dose of 110 mg in patients 12 years of age and older with severe eosinophilic asthma. The primary endpoint is the frequency of all adverse events including serious adverse events experienced in patients administered sc reslizumab. The study design includes standard assessments that will help inform the overall safety profile of reslizumab, as well as adverse events of interest including systemic reactions (including anaphylaxis and administration site reactions), malignancy, infections (including parasitic helminthic and opportunistic infections), ADA, and musculoskeletal/CPK abnormalities. This comprehensive data collection methodology will allow for a robust analysis of patient safety during the study.

3. STUDY DESIGN

3.1. General Design and Study Schematic Diagram

This is a global, multicenter, OL extension study to obtain additional long-term safety data of reslizumab treatment administered sc at a fixed dose of 110 mg in patients 12 years of age and older with severe eosinophilic asthma.

The study consists of a screening/baseline visit (V1; seamless rollover patients; conducted on the same day as the end-of-treatment [EOT, week 52 or week 24, respectively] visit for patients who finished either Study 30025 or 30027) or a standalone screening visit (V0) for patients who did not seamlessly rollover from Study 30025 or 30027 (had a gap between placebo-controlled study EOT and start of OLE; Section 4.1 and Appendix B.1), followed by an OL treatment period, an EOT visit (V_{EOT}), a follow-up telephone call (V_{FU}) at 12 weeks after the EOT visit, and an EOS visit (V_{EOS}) for immunogenicity testing 19 weeks after the final dose of study drug administration. The duration of the OL treatment period will be 9 months (36 weeks).

Study patients will be deemed eligible only if they meet all inclusion criteria and no exclusion criteria are fulfilled. Patients currently enrolled in Studies 30025 and 30027 will be required to complete their respective treatment periods to be eligible for this study. In addition, adolescents (patients 12 through <18 years of age) from Study 30025 must also complete the 12-week early follow-up visit (off study drug) before transferring to this OL study.

There may be a gap in study drug administration for some patients due to completion of Study 30025 or 30027 before the initiation of the OL extension study (non-seamless rollover). Patients with a gap between the EOT visit for Study 30025 or 30027 will complete a V0 screening visit. Adolescents (a patient 12 through <18 years of age) from Study 30025 can complete the V0 screening visit of Study 30066 the same day as the 12-week early follow-up visit for Study 30025. Any blood tests completed by adolescents at the 12-week early follow-up visit for Study 30025 can be used for the V0 screening visit of Study 30066 and do not need to be repeated. Any patient who did not rollover seamlessly from Study 30025 or 30027 will participate in a 7-day run-in period where baseline measures for asthma control and spirometry will be established. This screening assessment and run-in period will be completed within the 2 weeks prior to visit 1.

During screening/baseline, informed consent (and assent for patients under 18 years of age according to local Institutional Review Board/Independent Ethics Committee [IRB/IEC] requirements) will be obtained. This will be conducted at the EOT visit of Study 30025 or 30027 (seamless rollover patients) or at the standalone screening visit (V0) for non-seamless rollover patients with a gap in study drug administration (those who have previously completed Study 30025 or 30027, but are not screened on the same day as the EOT visit).

During the treatment period, patients will receive reslizumab by sc injection at a dosage of 110 mg every 4 weeks (28 days \pm 7 days) for 32 weeks in the study center. Patients will return to the study center every 4 weeks relative to baseline during OL treatment.

After study drug administration, each patient will remain at the study center for a minimum of 1 hour for observation. If during post-study drug observation the patient develops clinical symptoms, vital signs should be collected and the patient should be assessed for anaphylaxis/hypersensitivity reactions as detailed in Section 7.1.6.1.1.

After each administration, the patient will be required to use a study-provided handheld electronic diary (eDiary)/spirometry device that will ask questions post-injection to evaluate for any new symptoms that may have developed during the 24-hour period after investigational medicinal product (IMP) administration. The patient will complete a question regarding new symptoms on the eDiary device the evening after the IMP administration and the following morning. This is in addition to the peak expiratory flow (PEF; AM and PM), FEV₁ measurements (AM only), and recording of rescue inhaler use that are performed every day during the treatment period.

A full physical examination will be completed at screening and at EOT. Other safety evaluations will be performed at every visit when the study drug is administered: adverse event inquiry, vital signs measurement, assessment of injection site, concomitant medication use, and urine pregnancy test. Additional evaluations, including clinical chemistry, hematology, and ADA measurements, will be performed throughout the study according to the schedule of procedures and assessments ([Table 1](#)). Patients will also be monitored for asthma exacerbations throughout the study (Section [6.1.1](#)).

Measurement of ADAs will be performed on samples collected at baseline and at weeks 8, 24, and 36 or early withdrawal visit to evaluate the potential long-term immunogenicity of sc reslizumab, and on samples collected at the EOS visit (19 weeks after the final dose) to evaluate immunogenicity after study drug washout. A blood sample will also be collected in the event of withdrawal from the study or upon observation of any severe hypersensitivity reaction (eg, anaphylaxis). An unscheduled sample can also be drawn after a serious adverse event if the investigator or sponsor considers appropriate. Drug levels may be measured in the serum samples collected for ADAs to help inform ADA analysis. If a patient is found to have a positive ADA status after at least 2 doses of study drug in this OL study, the patient may be scheduled to complete an EOT visit. This testing may be done to enhance early data collection on potential washout samples. A summary of ADA results in previous clinical experience is outlined in Section [1.2.2.4](#).

[figure not shown]
An unscheduled visit may be performed at any time during the study at the patient's request or as deemed necessary by the investigator. The date and reason for the unscheduled visit as well as any other data obtained (eg, adverse events, concomitant medications and treatments, and results from

procedures or tests) will be recorded on the case report form (CRF) and noted within the patient's source notes.

Study procedures and assessments with their time points are shown in [Table 1](#).

The study schematic diagram is presented in [Figure 1](#).

Figure 1: Overall Study Schematic Diagram

DB=double-blind; BL=baseline; EOS=end of study; EOT=end of treatment; F/U=follow-up; ICS=inhaled corticosteroids; IP=investigational product; n=number; Q=every; SC=subcutaneous; V=visit; W=week

3.2. Planned Number of Patients and Countries

Approximately 360 patients will be enrolled in this study who have rolled over to this OL extension study from their participation in Studies 30025 and 30027.

The study is planned to be conducted in approximately 12 countries in approximately 140 investigational centers (centers that participated in Studies 30025 and 30027). The study is expected to start in March/Q1 2017 and last until approximately November/Q4 2018.

3.3. Justification for Study Design and Selection of Population

This study is a global, multicenter, OL, extension study to obtain additional long-term safety data of reslizumab treatment administered sc at a fixed dose of 110 mg in patients 12 years of age and older with severe eosinophilic asthma. This study will increase the length of patient exposure for patients previously exposed to reslizumab for up to an additional 9 months beyond the placebo-controlled studies (Studies 30025 and 30027).

The population selected for this study is considered representative of the asthma population with severe eosinophilic asthma. This study will enroll male and female patients 12 years of age and older with severe eosinophilic asthma who were randomized and completed the treatment period for a Phase 3 clinical study of reslizumab 110 mg sc (Studies 30025 and 30027). Note that adolescents (patients 12 through <18 years of age) from Study 30025 must also complete the 12-week early follow-up visit (off study drug) before transferring to this OL study.

3.4. Stopping Rules for the Study

The study may be terminated by the sponsor at any time for reasons including, but not limited to, a safety concern.

Other than pregnancy, there are no formal rules for study drug discontinuation in this study due to safety concerns. During the conduct of the study, serious adverse events and adverse events of special interest will be reviewed by the sponsor (Section 7.1.5.3.2) as they are reported from the investigational center to identify safety concerns.

If a patient is found to have a positive ADA status after at least 2 doses of study drug in this OL study, the patient may be scheduled to complete an EOT visit. This testing would be done to enhance early data collection on potential washout samples.

The investigator and/or sponsor can withdraw a patient from the study for reasons including, but not limited to, a change in the medical condition or an adverse event that alters the patient's benefit/risk (eg, pregnancy, a related severe hypersensitivity reaction, or related severe myalgia/muscle event), a protocol violation or deviation as defined in Section 7.1.9 or Section 7.3, or noncompliance.

A patient may discontinue participation in the study at any time for any reason (eg, lack of efficacy, consent withdrawn, or adverse event).

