8. OTHER ASSESSMENTS

8.1. Immunogenicity Testing

Immunogenicity of reslizumab sc administration will be assessed by qualified study personnel by evaluating the following:

- ADA measurement at baseline and at weeks 8, 24, and 36 or early withdrawal visit to evaluate the long-term immunogenicity of sc reslizumab
- ADA measurement at EOS visit (19 weeks after final dose) to evaluate immunogenicity after study drug washout

Blood samples (5 mL) for the assessment of ADA response will be taken before dosing at the time points indicated in [Table 1](#). A blood sample will also be collected in the event of withdrawal from the study or upon observation of any severe hypersensitivity reaction (eg, anaphylaxis). An unscheduled sample can also be drawn after a serious adverse event if the investigator or sponsor considers appropriate. Drug levels may be measured in the serum samples collected for ADAs to help inform ADA analysis.

Samples will be collected into labeled serum separator tubes and inverted slowly at least 5 times to thoroughly mix the blood with the clotting activation agent. Labels for samples should include study number, patient number, period, custom identification (ID), and nominal visit. Blood samples will be left standing upright at room temperature (20°C to 25°C) to clot for approximately 30 to 60 minutes. Samples should then be centrifuged at a minimum of 1500g for approximately 10 minutes at 4°C until clot and serum are well separated. Samples may be centrifuged at ambient temperature at 1500g for 10 minutes as long as measures are taken as appropriate to maintain ambient temperature during centrifugation.

Separated serum will be transferred, in approximately equal portions, into 2 labeled cryovial tubes (primary Aliquot A and back-up Aliquot B) and stored in an ultra-low freezer at -65°C or lower until they are shipped to a central or bioanalytical laboratory with temperature monitoring. Sample labels should include patient number, custom ID, study number, nominal visit or week, and indication that it is an ADA sample aliquot (A or B). Storage at -15°C to -20°C should not exceed 60 days if a freezer with a temperature of -65°C or lower is not available. The listed temperatures must be maintained. The actual times and dates of sampling will be recorded on the CRF.

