8.1.1. Shipment and Analysis of Samples

Serum samples for immunogenicity assessments for all patients will be shipped from the investigational center to the central laboratory, where they will be stored until shipped to the sponsor or its designee for analysis. Samples will be stored in an upright position at $\leq -65^{\circ}\text{C}$ until assayed. The central laboratory will be notified before the shipment of the samples and will be sent the shipping information when the samples are shipped. Aliquot set A samples will be transported with a temperature data logger and frozen with sufficient dry ice by next-day courier to the central laboratory.

Aliquot set B samples will either be sent to the same laboratory as that for aliquot set A on a later day by next-day courier or be retained at the investigational center until the study is completed (unless shipment to another facility is requested by the sponsor).

Samples from reslizumab-treated patients will be analyzed for ADA using appropriately validated methods. The ADA serum samples may be used to measure serum drug concentration if necessary to help ADA analysis. Timing of the initiation of sample analysis will be determined by the Teva Pharmaceuticals bioanalytical department representative responsible for the bioanalysis. The bioanalytical team will not be blinded for this analysis.

Additional details regarding the collection, handling, and shipment of samples for measurement of ADAs are provided in the investigator laboratory manual and its associated specimen collection summary. Further details can be found in [Appendix P](#).

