Unscheduled blood samples for ADA assessment will also be obtained from all patients (inside and outside of the United States) experiencing a serious adverse event, an adverse event leading to withdrawal, an observation of any severe hypersensitivity reaction (eg, anaphylaxis), or an exacerbation of asthma symptoms.

If a potentially clinically significant CPK level ($\geq 3.1 \times$ upper limit of normal [ULN]) occurs, the patient should attend an unscheduled visit for a physical examination, as well as additional testing, if indicated per investigator judgement.

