**4.4. Study Days and Visits**

Study days will be numbered relative to the first day of study drug administration. The start of treatment (day 1) is defined as the date on which a patient takes the first dose of study drug in this study. Days will be numbered relative to study start (ie, ..., -2, -1, 1, 2, ...) with day 1 being the start of study drug and day -1 being the day before the start of study drug).

For safety-by-visit summaries, if there are multiple assessments at a post-baseline visit then the last non-missing assessment at that visit will be used for the summary. This includes assessments at the scheduled and unscheduled visits.

For efficacy by-visit summaries, only the assessments at the scheduled visit will be summarized. The assessments at unscheduled visits will only be listed. For the purpose of the efficacy analysis, assessments collected at an early termination visit will be considered as the next scheduled visit for that assessment if at least 3, but no more than 5 weeks, elapsed since the date of the last dose of study drug.

“Endpoint” for safety and efficacy analyses summaries is the time point when the last observation was obtained during the treatment period. For patients who completed treatment in this study, the treatment period will be defined from the first dose of study drug to the end of treatment (week 36) visit. For patients who prematurely discontinue treatment, the treatment period will be defined from the first dose of study drug to the last dose of study drug + 4 weeks.

For summaries of diary data and handheld spirometry data, the day used for analysis will consist of the evening assessment for the day and the morning assessment for the following day, as illustrated in [Table 1](#). Weekly average data will be generated using 7-day window intervals derived based on these analysis days.

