## 8. SAFETY ANALYSIS

### 8.1. General

The safety analysis set (Section 3.2) will be used for all safety analyses unless otherwise noted. Summaries will be presented by double-blind treatment group in the previous studies 30025 and 30027 (placebo and reslizumab) and for all patients (ie, total), unless otherwise noted.

For continuous variables, descriptive statistics (n, mean, SD, SE, median, minimum, and maximum) will be provided. For categorical variables, patient counts and percentages will be provided. Categories for missing data will be presented if necessary.

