### 8.3. Adverse Events

Adverse events will be coded using the Medical Dictionary for Regulatory Activities (MedDRA); the final version number will be indicated in the summary tables.

On-treatment adverse event summaries will be presented by previous double-blind treatment group and for all patients, based on events with onset during the treatment period. If the AE start date is missing or partial, the event will be considered on-treatment unless there is evidence to the contrary (eg, month and year of AE start is present and is less than the month and year of the first dose of study drug). Post-treatment adverse events with onset during the follow-up period (ie, AE start date greater than the upper bound of the treatment period, as described in Section 4.4 previously) will be summarized separately.

Summaries will be presented by SOC and/or PT for all adverse events (overall and by severity), adverse events determined by the investigator to be related to study treatment (overall and by severity), serious adverse events, adverse events causing discontinuation from study treatment, and non-serious adverse events. Treatment related adverse event summaries will include events with missing relationship to study drug. For summaries by severity, patients will be counted at the greatest reported severity. Adverse events missing the flag indicating a serious adverse event will be excluded from the summary of serious adverse events, but included in the summary of non-serious adverse events.

In addition, adverse events that begin within 24 hours after study drug injection and injection-site adverse events (as recorded on the CRF) will each be summarized separately.

A summary for the most common adverse events (incidence  $\geq 2\%$  for all patients) will also be presented. Adverse events will additionally be presented for subgroups defined in Section 3.3.

All adverse events, including events with onset prior to the first dose of reslizumab in this study, will be included in the patient listings. The mapping of MedDRA dictionary terms for adverse event descriptions will also be provided.

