## 11. IMMUNOGENICITY ANALYSIS

The immunogenicity assessments for this study include the following:

- ADA measurement at baseline and at weeks 8, 24, and 36 or early withdrawal visit to evaluate the long-term immunogenicity of sc reslizumab
- ADA measurement at EOS visit (19 weeks after the final dose) to evaluate immunogenicity after study drug washout

Two types of antibody assay will be performed, an immunogenicity status assay (ADA) and neutralizing antibody assay (NAb). For the ADA assay, a screening assessment will be performed which produces a positive or negative result. For samples with a positive result, a neutralizing antibody assay will be performed, which also produces a positive or negative result; a titer value will be obtained to quantify the degree of binding.

A patient will be classified as having a treatment-emergent ADA response if a sample tested positive at any of the post-baseline time points but not at the baseline time point, or if the post-baseline ADA titer increased  $\geq 4$ -fold from a positive baseline ADA sample (Shankar et al 2014). In this open-label extension study, the baseline sample data for the purpose of analysis will be derived from the pre-dose samples obtained on the DOR in the previous study (30025 or 30027).

Anti-reslizumab antibody data, including neutralizing antibody and titer results for patients who have tested ADA positive, will be listed. The number of patients with positive/negative results will be summarized at each scheduled visit by previous double-blind treatment group and for all patients, if appropriate. ADA status will be correlated with variables of efficacy and safety via examination of eosinophils and adverse events, respectively, by ADA status (positive, negative).

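### Adverse events are to be compared by ADA status without exposure by ADA status, although only ADA-positive patients can be moved to an early end-of-treatment visit

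*Protocol*

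**What the plan says.** Protocol 3.4, repeated in 3.1 and 4.3 and in SAP 2.1, provides that for a patient with "positive ADA status after at least 2 doses of study drug in this OL study, the patient may be scheduled to complete an EOT visit". The stated purpose is to obtain washout samples early. The wording is permissive, and ADA-negative patients have no corresponding option.

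For patients who discontinue early, SAP 4.4 states that "the treatment period will be defined from the first dose of study drug to the last dose of study drug + 4 weeks". On-treatment adverse event summaries under SAP 8.3 are "based on events with onset during the treatment period"; later events are summarised separately.

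SAP 11 states that "ADA status will be correlated with variables of efficacy and safety via examination of eosinophils and adverse events", by ADA status (positive, negative). It names no measure and does not say whether on-treatment or all events are meant. The general rules in SAP 4.1 and 8.1 then apply: "For categorical variables, patient counts and percentages will be provided". SAP 8.2 summarises total patient-years, but only by previous double-blind group and for all patients.

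Two further provisions matter:

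- **Sampling.** Protocol Appendix B, under unscheduled visits, says "Unscheduled blood samples for ADA assessment will also be obtained from all patients" who have a serious adverse event, an adverse event leading to withdrawal, a severe hypersensitivity reaction or an asthma exacerbation. Protocol 8.1 is weaker on serious events: "An unscheduled sample can also be drawn after a serious adverse event if the investigator or sponsor considers appropriate".
- **Assay timing.** Protocol 8.1.1 leaves it open: "Timing of the initiation of sample analysis will be determined by" the sponsor's bioanalytical representative.

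**The concern.** The grouping variable can itself change how long a patient is observed. A patient who tests positive may leave early and so has less time in which to record an event. A crude percentage treats 12 weeks and 36 weeks of observation alike, so part of any difference between ADA groups would reflect follow-up rather than antibodies.

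Immunogenicity of the subcutaneous form is a stated assessment of this study, and adverse events by ADA status is the planned safety look at it. SAP 2.5.1 has all planned outputs produced for the interim report that supports the licence submission. A table that mixes ADA effect, follow-up length and sampling intensity is hard to interpret there.

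**Working it through.** The plan gives no figure to reproduce: the study is descriptive and its roughly 360 patients are the expected rollover. What follows is an illustration.

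**Inputs from the documents**
- Treatment period 36 weeks, doses every 4 weeks from week 0 to week 32 (Protocol 3.1, Table 1).
- On-treatment ADA samples at weeks 8, 24 and 36, drawn before dosing (Protocol 8.1).
- Window for early stoppers: last dose + 4 weeks (SAP 4.4).
- ADA incidence in the iv programme 5% (Protocol 1.2.2.4); the sc rate is not given. 5% of 360 = 18 patients; an assumed 2% to 20% would give 7 to 72.

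**Assumptions**
- Constant hazard, equal in ADA-positive and ADA-negative patients.
- 36-week risk R = 0.30.
- First positives split equally over weeks 8, 24 and 36. A week-36 positive cannot be stopped early.

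**Step 1: effect of early exit**

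λ = −ln(1 − 0.30)/36 = 0.00991 per week; risk over T weeks = 1 − exp(−λT).

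- Fast result (no further dose after the positive sample's visit): windows of 12, 28 and 36 weeks, risks 0.112, 0.242 and 0.300, mean 0.218. If all eligible patients stop, the ratio is 0.218/0.30 = 0.73.
- Two more doses before the result: windows of 20, 36 and 36 weeks, risks 0.180, 0.300 and 0.300, mean 0.260. Ratio 0.260/0.30 = 0.87.

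If a fraction f stops, the ratio is 1 − f × (1 − ratio with all stopped):

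| Share of eligible patients stopped | Fast result | Two more doses |
|---|---|---|
| None | 1.00 | 1.00 |
| A quarter | 0.93 | 0.97 |
| Half | 0.86 | 0.93 |
| All | 0.73 | 0.87 |

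The true ratio is 1.00 throughout. A person-time rate returns 1.00 in every cell, because the hazard is λ in both groups (0.517 first events per patient-year).

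**Step 2: does the choice of event window remove the effect?**

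No. The follow-up call is timed from the EOT visit, so early exit also shortens total follow-up. For an exit with a 12-week on-treatment window, adding 12 weeks of follow-up gives 24 against 48 weeks: risks 0.212 and 0.378, ratio 0.56. For that patient the on-treatment ratio is 0.112/0.300 = 0.37. The shortfall is smaller but present.

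**Step 3: the opposite mechanism**

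Assume no ADA effect, four scheduled samples, and a per-sample chance q of a positive with 1 − (1 − q)⁴ = 0.05, so q = 0.0127. Each patient with a trigger event has one extra sample. The chance of being ADA-positive is then 1 − (1 − q)⁵ = 0.062 with a trigger event and 0.050 without. Among patients so classified:

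- R = 0.30: event percentage 34.7% in positives and 29.7% in negatives, ratio 1.17.
- R = 0.06 (the iv serious adverse event incidence, Protocol 1.2.2.2.2): 7.3% and 5.9%, ratio 1.24.

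This applies to trigger events only. Longer follow-up also gives more chances to test positive, which works in the same direction.

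**Step 4: information available to a time split**

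With 18 positives, 6 at each visit, time after the first positive sample is 6 × (28 + 12 + 0) = 240 patient-weeks if nobody stops, or 4.6 patient-years. It is 6 × (4 + 4 + 0) = 48 patient-weeks, or 0.9 patient-years, if all eligible patients stop on a fast result. Expected events with no ADA effect are 240λ = 2.4 and 48λ = 0.5.

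**The case against.** **The measure and window are inferred.** SAP 11 speaks only of an examination, and Protocol 9.7 adds a condition of appropriateness. This stands as a limit on the claim. Percentages are nevertheless the SAP's general default, and step 2 shows that the shortening carries over to either window.

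**Use of the option is unknown.** It is discretionary, and the text implies rather than states that dosing stops. Samples go through a central laboratory and assay timing is open, so the fast-result column may be unrealistic. This stands too; with two more doses and a quarter stopped, the shift is only 3%.

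**Most information survives.** Adverse events and ADA results are listed, post-treatment events are summarised, and withdrawal reasons are tabulated (SAP 5.2, 8.3, 11). With about 18 positives, patient-level review will be the most informative tool. That is correct, and it is why the point is minor. It does not justify leaving follow-up out of a summary that the SAP commits to.

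**A stronger reading is tempting:** that the plan would hide or reverse a real ADA-related excess. The documents do not support it. They report no association between ADA and adverse events for the iv form (Protocol 1.2.2.4), give no sc data, and fix neither uptake nor assay timing. If a doubled hazard is assumed, much of the shortfall from 2 exists with nobody stopped: the crude ratio is 1.70 if the excess runs from day 1 and 1.28 if it starts at the first positive sample. That part is not caused by early exit.

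**Conclusion.** The concern holds as a minor point. Follow-up can differ by ADA status by design, and no planned output shows exposure by ADA status. With equal hazards and a 30% risk, full use of the option lowers the crude ratio to between 0.73 and 0.87, and use by a quarter lowers it to between 0.93 and 0.97. These figures rest on a constant hazard, the assumed timing of first positives and an assumed uptake.

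A reader might infer that the comparison is biased downward overall. That does not follow: event-triggered sampling can raise the ratio by a similar amount, so the net direction is unknown. Nor are events lost. The gap is confined to the summary by ADA status; the primary all-patient adverse event summary is untouched.

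**What to change.** In SAP 11:

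1. Show patient-years by ADA status. Beside the counts and percentages, report adverse events by ADA status as events per 100 patient-years and as first events per 100 patient-years at risk. State which event window is used.
2. As a supportive view, split time and events in ADA-positive patients at the first positive sample, counting earlier time as ADA-negative. Count patients already positive at V1 as positive from day 1; this can occur because the ADA baseline is the parent-study sample (SAP 4.2.7). The split is needed because whole-period rates do not recover an excess that begins only at the first positive sample: with a true ratio of 2 they give 1.37 with nobody stopped and 1.11 with all eligible patients stopped.
3. Report how many patients were moved to EOT because of ADA positivity.
4. In the listing, show adverse event onset relative to the last negative and first positive sample.

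Keep the SAP's classification from all samples as primary, and show a scheduled-samples-only grouping as a sensitivity view. Making the latter primary would class a patient whose only positive sample was drawn at an anaphylaxis as ADA-negative.

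**Cost:** a few table rows, added listing information and SAP wording. The count in item 3 needs the reason to be identifiable from the recorded withdrawal reason or a separate code. Nothing changes in the clinical option or the sampling schedule. The rates will be imprecise: about 18 positives at the iv rate give roughly 0.9 to 4.6 patient-years after the first positive sample, and 0.5 to 2.4 expected events at 30% risk with no ADA effect. Rare events will still rest on the listing, and ADA onset is known only to the sampling interval, up to 16 weeks.
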